**Sponsor/Quotient Sciences Confidential**

---

warranted or may agree to reduce the dose with no limit on the possible extent of reduction. Any decision to investigate an intermediate or reduced dose level will be fully documented.

The decision to proceed to the next dose level will be based on safety, tolerability and available PK data. The following data are required:

- AEs
- Vital signs
- Safety laboratory results
- ECGs
- Physical examination findings
- Plasma concentrations of MMV367
- Interim PK parameter estimations (Tmax, Cmax, AUC(0-24), AUC(0-48), AUC(0last), AUC(0-inf), T1/2, where possible and appropriate)

Rules for dose decision are as follows:

- Dose increments between SAD cohorts will be a maximum of 3-fold and dose escalation may be halted in the SAD cohorts if an exposure plateau appears to have been reached
- Dose increments between multiple dose optional cohorts will be no more than 3-fold
- No dose selected for SAD or MAD will be expected to result in a mean group exposure at the next dose level (based on predicted human PK and assuming dose linearity) greater than AUC(0-inf) 376 µg.h/mL, and Cmax 23.8 µg/mL based on the NOAEL in dogs and the corresponding human therapeutic exposure
- The predicted exposure (AUC(0-inf)) of the cumulative dose after a 3-day treatment will not exceed that of a single dose evaluated in Part 1 which is safe and well tolerated
- The study will be halted (see Section 8.5 of the study protocol) and thus a further dose decision will not be made if:
  - One or more participants experience an IMP-related serious AEs (SAE)
  - Two or more participants experience an IMP-related severe or clinically significant non-serious AE at the same dose level/same cohort

If, following review by the SAC it is deemed acceptable to continue dose escalation above the defined maximal dose or exposure limit, a substantial amendment with relevant data will be submitted for approval to the Medicines and Healthcare products Regulatory Agency (MHRA) and ethics committee (EC).

*Progression from Part 1 (SAD) to Part 2 (Food Effect).*

For the dose level decision to be made for Part 2, data must be available from a minimum of 6 participants who have completed the planned safety assessments up to 7 days after dosing and planned PK assessments up to 144 h after dosing (to ensure at least 4 participants had received active IMP), at a relevant dose level in Part 1. A “relevant dose level” is defined as a dose that demonstrated acceptable safety/tolerability (i.e., exposure levels at which no study specific criteria stopping dose progression and/or escalation were met) at a mean exposure that is not anticipated to be exceeded by the

## **Sponsor/Quotient Sciences Confidential**

---

dosing regimen in Part 2, taking into account a potential bioavailability increase to 100% after a high-fat breakfast.

### *Progression from Part 1 (SAD) to Part 3 (Multiple Dose).*

For the dose level decision to be made for Part 3, data must be available from a minimum of 6 participants who have completed the planned safety assessments up to 7 days after dosing and planned PK assessments up to 144 h after the final dose (to ensure at least 4 participants had received active IMP), at a relevant dose level in Part 1. The total dose in Part 3 ( $3 \times$  QD dose) will not exceed a dose of MMV367 administered and evaluated as a single dose in Part 1, and the predicted exposure will not exceed an exposure observed and determined to be safe in Part 1. If a less than dose-proportional increase in exposure is observed in Part 1 (SAD), the proposed dose(s) for Part 3 may be adjusted to ensure the equivalent exposures between SAD and MAD.

#### **8.2.1 Criteria for Sentinel Dosing Decisions**

For all cohorts following a sentinel design (Parts 1 and 3) the decision to proceed with the main group will be made by the investigator, based on safety data until 96 h postdose (Part 1) or 96 h post-final dose (Part 3) in the sentinel participants. The investigator or medically qualified designee who is familiar with the study protocol and IB, and medical monitor or delegate (with approval from the sponsor's medical director or delegate) will decide whether to proceed with dosing the remaining participants in the cohort.

#### **5.3 Study Sample Size**

For Parts 1 and 3, the primary objective is an initial assessment of safety and each treatment group is therefore limited to 6 participants receiving active IMP. Administration of MMV367 to 6 participants at each dose level provides a 47%, 62%, 74%, or 82% probability of observing at least 1 occurrence of any AE, with a true incidence rate for a given dose group of 10%, 15%, 20%, or 25%, respectively.

Furthermore, it is assumed that pooling the data for the 2 participants who receive placebo in each cohort will provide an adequately sized control group to assess a possible drug effect on safety laboratory tests, vitals and ECG parameters.

Part 2 is a pilot evaluation designed to determine whether MMV367 PK is impacted by high-fat food. Historically, 8 participants have proven sufficient to characterise the preliminary effects of food on safety and PK of a new chemical entity in healthy participants. Therefore, a sample size of 8 is considered adequate at this stage of drug development.

#### **5.4 Randomisation (including Replacement Subjects)**

Parts 1 and 3 will be randomised (IMP/placebo) and double-blinded. Part 2 will be randomised (fed/fasted) and open-label. A randomisation schedule will be produced for each study part. Instructions to dispense and dose will be produced prior to dosing using the randomisation schedule and will be retained in the ISF.

For Part 2, the original randomisation schedule and proof of quality control procedures will be held by the Data Sciences department at Quotient until the study is archived, at which time the randomisation materials will be retained in the ISF.

**Sponsor/Quotient Sciences Confidential**

Using computer-generated randomisation schedules, participant numbers will be allocated to treatment regimens in a 6:2 ratio (MMV367:placebo) in each cohort (Part 1 or Part 3). In Part 2, the allocation will be balanced with 8 participants assigned to receive MMV367 in both the fed and fasted states. Participants will be randomised to 1 of 2 treatment sequences (Regimen 6/Regimen 7 or Regimen 7/Regimen 6) on Day 1 prior to dosing in the first period.

For participants in Parts 1 and 3, a sentinel group of 2 participants will be dosed ahead of the remaining participants in each cohort. For each cohort, using a computer-generated randomisation schedule, the first 2 participant numbers will be allocated to active or placebo in a 1:1 ratio (i.e., 1 participant will be randomly assigned to receive MMV367 and 1 participant will be randomly assigned to receive placebo). The remaining 6 participant numbers will be allocated to active or placebo in a 5:1 ratio (i.e., 5 participants will be randomly assigned to receive MMV367 and 1 participant will be randomly assigned to receive placebo).

Participants will be randomised immediately before administration of the first dose.

#### **5.4.1 Participant Numbers**

Participant numbers will be allocated on the morning of dosing according to the code 101 to 140 in Part 1, 201 to 208 in Part 2, and 301 to 324 in Part 3 using the lowest number available. Replacement participants will be allocated participant numbers 901 to 940 in Part 1, 801 to 808 in Part 2 and 701 to 724 in Part 3, where the last two digits are the same as those of the original participant (e.g., if Participant 105 withdraws, the replacement will have Participant Number 905 and will receive the same regimen as Participant 105).

In Part 1, up to 2 replacement participants may be used per cohort. The maximum number of participants that may be dosed is 50 (8+2 per cohort). In Part 2, up to 4 replacement participants may be enrolled into the study. The maximum number of participants that may be dosed in Part 2 is 12 (8+4). In Part 3, up to 2 replacement participants per cohort (if optional cohorts are utilised) may be enrolled into the study. The maximum number of participants that may be dosed is 30 (8+2 per cohort).

Any participant withdrawn due to an IMP related AE will not be replaced.

Participants withdrawing for other reasons may be replaced as required by agreement between the investigator and sponsor to ensure sufficient evaluable participants. Participant numbering by study part and cohort is provided in [Table 4](#).

**Table 4 Participant Numbers**

Study Part	Cohort	Participant Numbers
1	1A	101–108
	1B	109–116
	1C	117–124
	1D	125–132
	1E (optional)	133–140
2	2A	201–208
3	3A	301–308
	3B (optional)	309–316
	3C (optional)	317–324

---

**Sponsor/Quotient Sciences Confidential**

---

## 5.5 Blinding Issues

Parts 1 and 3 of the study are double-blinded. Treatment assignment will not be known to the participants, the sponsor or the staff who are involved in the clinical evaluation of the participants and the analysis of data. If appearance matching of the placebo is not possible then masking and/or unblinded dosing teams will be used to preserve the study blind. Further details of these steps will be contained in the study specific blinding plan, which will be approved prior to dosing. The randomisation schedules and disclosure envelopes will be generated by an unblinded statistician at Quotient according to Quotient's SOPs. The unblinded statistician will not be involved in any decisions relating to populations for analysis prior to unblinding. Prior to database lock and unblinding, all original randomisation materials, including the original final signed and dated randomisation schedule, will be held by the Quality Assurance (QA) department at Quotient. The Data Sciences department will not have access to the randomisation schedule before database lock and unblinding.

Interim PK parameter estimations will be performed using bioanalytical data applied with participant aliases in order to maintain the study blind.

There may be instances where interim PK data have the potential to be treatment revealing e.g., missed blood sampling occasions. In these cases, every effort will be made by the pharmacokineticist to maintain the study blind by appropriate presentation of data to the study team. Data demonstrating extremes of exposure will always be presented, regardless of the potential to reveal the study blind. To permit selection of the dose level, individual data may be made available in full if judged necessary by the investigator or sponsor regardless of the potential to reveal study blind.

The unblinded Qualified Person or designee at the clinical site will receive a copy of the final randomisation schedule for preparation of the study drug and preparation of the instructions to dispense and dose. A copy of the randomisation schedule will also be made available to the laboratory performing the bioanalysis to allow selective analysis of drug concentrations (for Parts 1 and 3) and to the pharmacovigilance provider for analysis of pharmacovigilance.

Two sets of disclosure envelopes (i.e., sealed envelopes containing individual participant randomisation details) will be provided. One set will be held in the clinical area and the other retained in the ISF. These may be used in the event of an emergency by the investigator or delegate. Any request for information on the randomisation schedule after initial issue must be made using a randomisation disclosure form, except in the case of emergency unblinding, which must be recorded on the emergency unblinding form. Access to study drug assignment will be immediately available if the investigator deems it necessary to break the study blind in the interest of a participant's medical safety, in case of a medical emergency, or if warranted during scheduled safety reviews. The medical monitor must be contacted within 24 h following disclosure of study drug assignment.

Details of any disclosure of the randomisation schedule will be documented and retained in the ISF. The sponsor will be notified if the study blind is broken.

Part 2 of the study is open-label and therefore blinding is not required.

**Sponsor/Quotient Sciences Confidential**

---

## **5.6 Unblinding procedures**

The study blind will be broken after the study database has been locked and the safety population has been defined. Any subsequent request for issue of the randomisation schedule prior to unblinding must be made using a randomisation disclosure form.

## **5.7 Maintaining the Blind During Interim PK Analyses**

The interim PK analysis/analyses in Part 1 and Part 3 will be performed on QC checked concentration data for MMV367 in plasma using nominal sampling times and doses. Data will be received with participant aliases applied to the concentration data in order to maintain the study blind.

There may be instances where interim data has the potential to be treatment revealing eg missed blood sampling occasions. In this case every effort will be made by the pharmacokineticist to maintain the study blind by appropriate restriction/modification of data presented to the study team, such as only presenting the summary statistics e.g., mean, SD, minimum, median, maximum, geometric mean and geometric CV% for both PK parameters and concentration data.

Data demonstrating extremes of exposure will always be presented, regardless of the potential to reveal the study blind. Further details can be found in the blinding plan.

# **6 Populations and Analysis Sets**

## **6.1 Safety Population and Safety Analysis Set**

The safety population and safety analysis sets will be defined separately for each study part.

The safety population will include all subjects who have received any amount of IMP.

The safety analysis set will be defined on a treatment basis and will include all safety data from the subjects included in the safety population who have received that treatment.

The safety population will be confirmed by Quotient with approval from MMV after database lock (Part 2) and prior to unblinding (Part 1 and Part 3) and will be summarised for the populations table and to determine the subjects to be included in the safety analysis set.

The safety analysis set will be confirmed by Quotient with approval from MMV at the same time as the relevant safety population and will be summarised for the analysis of demographic and baseline characteristics, and all safety data.

## **6.2 Taste Population and Taste Analysis Set**

The taste population will include all subjects who have received at least one regimen (i.e., active dose or placebo), in Part 1, and held it in their mouth for approximately 10 to 15 seconds. Participants will have also completed the taste questionnaire for a regimen and have no relevant protocol deviations for any taste test or AEs which confound the taste assessment.

The taste population will be determined by Quotient with approval from MMV after database lock and will be used for the taste tables and to determine the participants to be included in the taste analysis set.

---

**Sponsor/Quotient Sciences Confidential**

---

The taste analysis set will be defined on a regimen basis and will include all relevant data from the participants included in the taste population who have received that test product.

The taste analysis set will be determined by Quotient with approval from MMV at the same time as the taste population and will be used for all summary tables and formal statistical analysis of taste data.

### **6.3 Pharmacokinetic Population and Pharmacokinetic Analysis Set(s)**

The PK population will be defined separately for study Parts 1, 2 and 3 and will include all subjects who have received at least one dose of IMP and who satisfy the following criteria for at least one profile:

- No missing samples or invalid post-dose analytical results at critical time points e.g., around Cmax
- No relevant protocol deviations that may impact the study objectives with respect to the PK endpoints
- No relevant AEs such as vomiting that suggest that the whole dose was not available for absorption for a particular participant

Handling of the urine concentration data is not currently a planned analysis in the CSR; however, should a validated method be developed and the urine concentrations be required to be reported by Quotient in Part 1, then the following should apply to the processing of the urine data. Any protocol deviations or AEs specific to the analysis of urinary PK parameters will be documented as an update to the PK population when urine data are available for analysis. Subjects who received placebo in Part 1 and 3 will not be included in the PK population.

The PK analysis set will be defined on a per-treatment basis and will include all relevant data from the subjects included in the PK population who have received that treatment.

In Part 1, individual subjects will be excluded from the PK analysis set where deemed appropriate such as if the participant's data for the treatment affected did not meet the bullet point criteria above, or other study emergent point related to PK analysis or interpretation.

In Part 2, individual participant profiles (i.e., treatments) will be excluded from the PK analysis set where deemed appropriate such as if the participant's data for the treatment affected did not meet the bullet point criteria above, or other study emergent point related to PK analysis or interpretation.

In Part 3, individual subjects will be excluded from the PK analysis set where deemed appropriate such as if the participant's data for the treatment affected did not meet the bullet point criteria above for at least one individual profile (i.e., day), or other study emergent point related to PK analysis or interpretation.

Individual participant profiles in Part 3 (i.e., days) will be flagged and excluded from the PK summary statistics where deemed appropriate such as if the profile in the day affected did not meet the bullet point criteria above, or other study emergent point related to PK analysis or interpretation.

The PK population and analysis set will be confirmed by Quotient with approval from MMV following derivation of all PK parameter estimates.

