## **Sponsor/Quotient Sciences Confidential**

---

If required, a PK analysis subset(s) will also be documented by Quotient, with approval from MMV, at the same time as the PK population and analysis set, if additional subjects are required to be excluded from the statistical analysis (i.e., to exclude subjects who have not received both the fed and fasted treatments in Part 2).

All enrolled subjects will be used for the PK data listings. The PK population will be used for the populations table. The PK analysis set and/or the PK analysis subset(s), if defined, will be used for the provision of PK summary tables and figures as well as the formal statistical analysis and will be documented as the same time as the PK population.

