**Sponsor/Quotient Sciences Confidential**

**Table 9 PK Parameter Flags and Footnotes**

Flag	Footnote
a	Adjusted rsq of regression (the goodness of fit statistic for the elimination phase) was <0.8
b	Period used for regression analysis was less than 2-fold the calculated half-life
c	Extrapolated portion of AUC(0-inf) >20%
d	Insufficient post-Cmax data points for estimation of lambda-z
e	Entire profile BLQ, no PK parameters could be calculated
f	Fewer than 3 consecutive measurable concentrations, AUCs not calculated
g	Measurable pre-dose values were observed, however were considered less than 5 % of Cmax (Part 2 only)

In the event that the adjusted rsq of regression is <0.8 ("a" flag) then lambda-z and parameter estimates derived using lambda-z and AUC(0-inf) will be deemed unreliable and will be flagged and listed but excluded from the summary statistics and formal statistical analysis.

In the event that the time period used for regression analysis is less than 2-fold the calculated half-life ("b" flag) T1/2 will be flagged, listed, and included in summary statistics and formal statistical analysis.

In the event that the extrapolated portion of AUC(0-inf) >20% ("c" flag), then AUC(0-inf) and parameter estimates derived using AUC(0-inf) will be deemed unreliable and will be flagged and listed but excluded from the summary statistics and formal statistical analysis.

In the event that there are insufficient post-Cmax data points (i.e., <3) for estimation of lambda-z ("d" flag) then lambda-z and parameter estimates derived using lambda-z and AUC(0-inf) will be reported as NC.

In the event that there are fewer than 3 consecutive measurable concentrations ("f" flag) then all AUC parameter estimates will be reported as NC.

In the event that measurable pre-dose values less than 5% of Cmax were observed ("g" flag), all parameter estimates for the profiles affected will be listed, flagged and included in summary statistics and formal statistical analysis.

Note: in the event that measurable pre-dose concentrations greater than 5% of Cmax are observed, requirements for additional flags and further action will be agreed with MMV and documented at the same time as the PK population.

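### One missing or invalid sample near the peak bars a Part 1 participant from every PK summary and the dose-proportionality model, although it affects mainly Cmax and Tmax

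*SAP*

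**What the plan says.** SAP 6.3 admits to the PK population participants who have received IMP and "who satisfy the following criteria for at least one profile". The first criterion is "No missing samples or invalid post-dose analytical results at critical time points e.g., around Cmax"; the others concern relevant protocol deviations and events, such as vomiting, that suggest incomplete absorption. The critical time points are not listed.

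The PK analysis set is drawn from that population, and exclusion from it is worded as a judgement:

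- Part 1: "individual subjects will be excluded from the PK analysis set where deemed appropriate such as if" the criteria are not met.
- Part 2: "individual participant profiles (i.e., treatments) will be excluded from the PK analysis set where deemed appropriate such as if" they are not met.
- Part 3: participants may be excluded, and single-day profiles "will be flagged and excluded from the PK summary statistics where deemed appropriate".

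On timing: "The PK population and analysis set will be confirmed by Quotient with approval from MMV following derivation of all PK parameter estimates". On use: "The PK analysis set and/or the PK analysis subset(s), if defined, will be used for the provision of PK summary tables and figures". The formal statistical analysis uses them too. Listings cover all enrolled participants.

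Elsewhere the SAP works parameter by parameter. In 9.1.3, when more than 20% of AUC(0-inf) is extrapolated, "AUC(0-inf) and parameter estimates derived using AUC(0-inf) will be deemed unreliable and will be flagged and listed but excluded" from summaries and analysis, while the rest of the profile stays. No flag in Table 9 concerns a gap near the peak. Section 9.1.2 treats absent concentrations as missing, and Table 8 keeps Cmax out of the lambda-z regression.

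**The concern.** The criterion is aimed at Cmax but acts on the whole profile. A lost sample at the peak leaves the observed Cmax and Tmax in doubt. It says almost nothing about the terminal slope and little about an area that runs to 144 h. By the SAP's own rules the non-compartmental analysis can still be run on such a profile.

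In Part 1 the population rule is categorical and each participant has one profile. The discretion in the later analysis-set sentence cannot readmit someone who never entered the population, so the two sentences do not fit together. In Parts 2 and 3 discretion does operate, but on whole profiles or participants, with the trigger undefined and the parameter values already known.

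At stake is the precision of secondary PK endpoints (AUC, CL/F, half-life, fed/fasted AUC ratio) in groups of 6 active participants, with a stated minimum of 4, and in a food-effect cohort of 8.

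**Working it through.** The SAP gives no PK precision figure. Its only sample-size figures are the chances of seeing at least one AE among 6 active participants, 1 − (1 − p)^6. For p = 10%, 15%, 20% and 25% this gives 46.9%, 62.3%, 73.8% and 82.2%, which agree with the stated 47%, 62%, 74% and 82%.

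**Step 1. Effect of a gap on each parameter.**

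Inputs from the documents: plasma times 0, 0.5, 1, 2, 3, 4, 5, 6, 8, 12, 24, 48, 72, 96 and 144 h (SAP Appendix 4, pre-dose set to 0); linear-log trapezoid (Table 8); predicted half-life 19 h (protocol 5.3.1.2).

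Assumed: a one-compartment oral profile, C(t) = ka/(ka − ke) × [exp(−ke·t) − exp(−ka·t)] up to scale, with ke = ln 2 / half-life; half-lives of 12, 19 and 40 h; ka of 0.3 to 2 per h, with 0.2 as a slow case; lambda-z from the last three points. The documents give no ka.

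One sample within two positions of the peak was deleted and the parameters recomputed. Worst absolute changes:

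| Parameter | ka 0.3 to 2 per h | ka 0.2 per h |
|---|---|---|
| AUC(0-inf), any half-life | 1.4% | 2.9% |
| AUC(0-inf), half-life 19 h | 1.0% | 2.3% |
| AUC over the first 24 h | 2.1% | 3.5% |
| Half-life | 0.0% | 0.0% |
| Cmax | 3.9% | 7.3% |

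The 24 h row bears on AUC(0-tau) in Part 3: a similar absolute error is a larger share of a shorter area.

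With three consecutive samples around the peak deleted, AUC(0-inf) falls by up to about 4% at ka 0.3 and by 7% to 12% at ka 0.2. Fast absorption is not wholly safe either: at ka 3 per h and half-life 12 h the fall is 6.5%. Half-life is still unchanged.

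**Step 2. Cost of losing the participant, Part 1.**

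The planned interval is the 90% CI for the slope β (SAP 9.6.1). Its half-width is t(0.95, N − 2) × s / √Sxx, with Sxx the sum of squares of log dose about its mean. Take constant s and 6 per dose level.

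- Four levels (100 to 1500 mg): N = 24, Sxx = 24.77, t = 1.717. Dropping one participant at 100 mg gives N = 23, Sxx = 22.56, t = 1.721. Ratio = (1.721/√22.56) / (1.717/√24.77) = 1.050.
- The same step at 300, 750 and 1500 mg gives 0.5%, 0.9% and 3.7%.
- Five levels (100 to 2000 mg): 4.9%, 0.8%, 0.2%, 1.4% and 2.4% from lowest to highest dose.

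The range is 0.2% to 5.0%, largest at the ends of the dose range.

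**Step 3. Cost of losing a pair, Part 2.**

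The half-width on the log scale is t(0.95, n − 2) × s × √[(1/n1 + 1/n2)/2].

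- n = 8 (4 + 4): 1.943 × 0.500 = 0.972.
- n = 7 (4 + 3): 2.015 × 0.540 = 1.088.
- Ratio: 1.088/0.972 = 1.12.

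At an assumed within-participant CV of 30%, the factor around the ratio goes from 1.33 to 1.38.

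**Step 4. How often.**

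The documents give no missing-sample rate. If three samples per profile count as critical and each is lost with probability 1%, 2% or 5%, the chance that a group of 6 has at least one affected profile is 1 − (1 − q)^18, or 17%, 30% or 60%.

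**The case against.** A reader might infer that the SAP drops such profiles automatically in every part. It does not. In Parts 2 and 3 a participant can stay in the population through another qualifying profile, and removal of the affected one is a judgement. Only the Part 1 population sentence is categorical. Excluded values also remain in the listings.

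A reader might also infer that a lost Part 2 profile always costs the pair. SAP 9.6.2 asks that participants complete both periods, and the example in 6.3 is of participants who did not receive both treatments. Someone dosed and sampled twice meets both wordings. An explicit rule on estimates in both periods exists only for AUC(0-inf), so the 12% is conditional.

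The precision loss can be put too high. The 90% CI of a single cohort's geometric mean would widen by 16% going from 6 to 5, but SAP 9.3 plans no such interval. The slope CI is the one reported, and it changes by 5.0% at most.

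Nor is AUC immune to gaps. Several consecutive losses can bias it materially, and no present flag would catch that, so a rule that always kept AUC would be worse than the current discretion in that case.

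Finally, samples to 96 h are taken in residence, in narrow windows and with priority over other procedures, so losses may be rare. One can add that 6.3 screens profile integrity and 9.1.3 screens estimate reliability, so they do not strictly contradict each other.

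All of this limits the size and reach of the point. None of it gives a reason to discard half-life, AUC and clearance for one lost peak sample in Part 1, or to leave the trigger undefined until the values have been seen.

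**Conclusion.** The point holds in a limited form. As written, one missing or invalid sample at a critical time near the peak takes a Part 1 participant out of every PK summary, figure and the power model. In Parts 2 and 3 it may take out a profile or a participant, by a decision made once the parameters are known.

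For a single gap the parameters lost needlessly are half-life (no change) and AUC, CL/F and Vz/F (AUC(0-inf) error at most about 1.4%, or 2.9% with slow absorption). The precision cost is modest: 0.2% to 5.0% on the Part 1 slope CI, and about 12% on the food-effect CI if the pair is lost.

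These sizes rest on a one-compartment shape, the assumed ka range, constant residual variance and full groups before the loss. The half-life result also needs the lambda-z points to lie after the gap. The case for change is that a better rule costs little, not that the present one would overturn a conclusion.

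**What to change.** Move the first criterion out of the population definition in SAP 6.3 and make it a flag in Table 9, with its handling in 9.1.3:

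- List the critical time points before unblinding, by nominal time or by position relative to the observed peak.
- For a single missing or invalid sample there, flag, list and exclude only Cmax, Tmax, Frel Cmax and AR Cmax for that profile. Keep AUC, T1/2, CL/F and Vz/F, subject to their existing flags.
- Pre-specify a limit, for example two or more consecutive missing samples around the peak, beyond which AUC and the parameters derived from it (CL/F, Vz/F, Frel AUC, AR AUC) are excluded as well. Set it with AUC(0-tau) in mind, since a 24 h area is more sensitive.
- Keep whole-profile exclusion for incomplete absorption of the dose and for relevant protocol deviations.
- State in 9.6.2 whether a participant with one excluded profile counts as having completed both periods.

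The cost is a few lines of text and one more flag, with no change to study conduct. The number analysed will differ between parameters, which the mock tables already accommodate, and a retained AUC will carry a small error from a single gap.
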